# 2.2.2.1. Part 2/Cohort 1 - PF-06747143 Combination in Fit Treatment Naïve AML Patients

Cohort 1 safety lead-in group (S1) will start with 10 mg/kg dose of PF-06747143 and may be escalated to up to 20 mg/kg (the MPD) or de-escalated to below 10 mg/kg based on the predefined DLT criteria (see Section 3.1.1.3) and emerging data. After completion of the S1 cohort, PF-06747143 will be administered in combination with intensive therapy (ie, 7+3 daunorubicin and cytarabine) as induction and continue during consolidation and in maintenance for up to a maximum of 6 months (6 cycles) starting from the completion of consolidation, until disease progression or relapse, patient refusal or unacceptable toxicity occurs (whichever comes first) in newly diagnosed treatment naïve fit AML patients. The expansion cohort (E1) will enroll up to 30 patients.

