# 2.2.2.2. Part 2/Cohort 2 – PF-06747143 Combination in Unfit Treatment Naïve AML Patients

Cohort 2 safety lead-in group (S2) will start with 10 mg/kg dose of PF-06747143 and may be escalated to up to 20 mg/kg (the MPD) or de-escalated to below 10 mg/kg based on the predefined DLT criteria (see Section 3.1.1.3) and emerging data. After completion of the S2 cohort, PF-06747143 will be administered in combination with a hypomethylating drug (ie, either azacitidine or decitabine, based on institutional guidelines) and may continue for up to 1 year (~12 cycles) from start of therapy or until disease progression or relapse, patient refusal or unacceptable toxicity occurs (whichever comes first) in newly diagnosed treatment naïve unfit AML patients). The expansion cohort (E2) will enroll up to 30 patients.

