#### **2.2.3. Summary**

Approximately 125-140 patients are expected to be enrolled in this study (approximately 30-50 patients in Part 1 (actual number of patients enrolled for Part 1 will depend upon tolerability of PF-06747143 and the number of dose levels required to identify the MTD) and approximately 87-102 patients in Part 2). The study will be conducted in approximately 4 sites for Part 1 and approximately 12-15 sites for Part 2.

Patients who complete the maximum number of cycles/months on study treatment (Section 3.1.2.2.1 and Section 3.1.2.2.2), demonstrate clinical benefit with manageable safety profile and are willing to continue receiving the assigned treatment may be given the opportunity to do so upon agreement between Investigator and sponsor and pending investigational product availability.

All patients who completed treatment will have a 60-day post dose follow-up period.

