**Progression Free Survival (PFS)** - is defined as the time from Cycle 1 Day 1 (C1D1) to first documentation of disease progression or to death due to any cause, whichever occurs first. Subjects last known to be 1) alive 2) on treatment or within the post-treatment follow-up period and 3) progression-free, are censored at the date of the last disease assessment that verified lack of disease progression. Subjects who start new anti-cancer treatment prior to the end of post-treatment follow-up period and have adequate baseline and on-treatment objective disease assessments without evidence of progressive disease are censored at the date of the last objective disease assessment. Subjects with inadequate baseline or no on-study disease assessments are censored at C1D1 unless death occurred prior to the first planned assessment (in which case the death is an event). Subjects with at least one on-study disease assessment who discontinue treatment without disease progression and without death within 28 days of discontinuation are censored at the date of the last objective disease assessment that verified lack of disease progression (if progression or death is within 28 days of discontinuation the progression or death is an event). Subjects with documentation of progression or death after an unacceptably long interval (>16 weeks) since the previous disease assessment will be censored at the time of the previous assessment.

PFS (days) = [progression/death date - C1D1 + 1].

• Overall survival (OS) is defined as the time from initial dose until death from any cause, and is measured in the intent-to-treat population.

More details of censoring are provided in Appendix 2.

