#### 11.2. APPENDIX 2: CENSORING DETAILS

Table 4. Progression Free Survival and Duration of Response

Situation	Date of Progression/Censoring 	Outcome		
Inadequate baseline assessment	Start date (C1D1)	Censored		
No on-study assessments	Start date (C1D1)	Censored		
Alive, on treatment  and no Progression	Date of last objective tumor assessment	Censored		
Progression Documented on or between scheduled tumor assessments prior to treatment discontinuation 	Date of first objective tumor assessment showing objective progression	Progressed (Event)		
Treatment discontinuation for undocumented progression	Date of last objective tumor assessment prior to discontinuation 	Censored		
Treatment discontinuation due to toxicity or other reason	Date of last objective tumor assessment prior to discontinuation 	Censored		
Death prior to first planned tumor assessment	Date of death	Death (Event)		
Death without objective progression prior to treatment discontinuation 	Date of death	Death (Event)		
Death or progression after 2 or more missed tumor assessments	Date of last objective tumor assessment prior to the event	Censored		

1: For date of censorship, if a tumor assessment takes place over a number of days (eg, superficial lesions one day, scans another), the last date is used as the assessment date.

**Table 5.** Time to Progression

Situation	Date of Progression/Censoring 	Outcome		
Inadequate baseline assessment	Start date (C1D1)	Censored		
No on-study assessments	Start date (C1D1)	Censored		
Alive, on treatment  and no	Date of last objective tumor assessment	Censored		
Progression	-			
Progression Documented on or	Date of first objective tumor assessment	Progressed (Event)		
between scheduled tumor assessments	showing objective progression			
prior to treatment discontinuation 				
Treatment discontinuation for	Date of last objective tumor assessment	Censored		
undocumented progression	prior to discontinuation 			
Treatment discontinuation due to	Date of last objective tumor assessment	Censored		
toxicity or other reason	prior to discontinuation 			
New anticancer treatment <28 days	Date of last objective tumor assessment	Censored		
after discontinuation of treatment	prior to new anticancer treatment			
without progression				
Death prior to first planned tumor	Start date (C1D1)	Censored		
assessment				

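### PFS and duration of response stop counting events 28 days after treatment ends, which conflicts with the PFS definition and the follow-up wording and may bias the estimates in either direction

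*SAP*

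**What the plan says.** Section 7.1 of the SAP runs PFS from Cycle 1 Day 1 to "first documentation of disease progression or to death due to any cause, whichever occurs first". The censoring text in the same section then uses two different windows.

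- **28 days.** Patients who stop treatment without progression and "without death within 28 days of discontinuation are censored at the date of the last objective disease assessment". The converse follows in brackets: "if progression or death is within 28 days of discontinuation the progression or death is an event".
- **Follow-up period.** Patients known to be alive, "on treatment or within the post-treatment follow-up period and 3) progression-free, are censored at the date of the last disease assessment". A further sentence, on new anti-cancer treatment, also refers to the end of the post-treatment follow-up period.

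Table 4 in Appendix 2 (section 11.2) covers both PFS and duration of response. Its row "Treatment discontinuation due to toxicity or other reason" censors at the last assessment before discontinuation, and so does the row for undocumented progression. Footnote 2 extends discontinuation by 28 days.

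Section 2.2.3 states: "All patients who completed treatment will have a 60-day post dose follow-up period".

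Treatment length is capped in two cohorts only. Cohort 1 continues "in maintenance for up to a maximum of 6 months (6 cycles") after consolidation. Cohort 2 "may continue for up to 1 year (~12 cycles) from start of therapy". Section 2.2.3 allows continuation beyond these limits by agreement. Part 1 and Cohort 3 treat until progression or relapse, refusal or unacceptable toxicity.

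**The concern.** A definition that includes every death does not fit a rule that ignores deaths from day 29 after stopping. Nor does a 28-day limit fit sentences that keep the patient under observation for the follow-up period. Two programmers could derive different PFS data from the same section.

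The rule matters because the SAP plans no hypothesis test and puts its emphasis on estimation. Kaplan-Meier medians with 95% intervals are thus the reported time-to-event results. Duration of response belongs to a Part 2 primary endpoint (section 2.4). Kaplan-Meier estimation assumes that censored patients have the same outlook as those still at risk. Patients who stop for toxicity, or for progression that was suspected but not documented, may well not.

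**Working it through.** **1. The passages side by side.** Take a patient who stops for toxicity, has no progression, and dies 45 days after stopping.

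| Rule | Outcome |
|---|---|
| PFS definition, section 7.1 | Event at death |
| 28-day sentence, section 7.1 | Censored at last assessment |
| Table 4 with footnote 2 | Censored at last assessment |
| Follow-up-period sentence, read with 60 days | Still observed at day 45, so the death would count |
| Overall survival, section 7.1 | Event at death (no 28-day limit) |

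One death is thus an OS event and a PFS censoring at an earlier date.

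**2. Size of the gap.** 60 − 28 = 32 days. Among patients event-free 28 days after stopping, the share with an event on days 29 to 60 is 1 − 0.5^(32/m), where m is an assumed exponential median in days:

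- m = 60: 1 − 0.5^(32/60) = 0.31
- m = 91: 1 − 0.5^(32/91) = 0.22
- m = 182: 1 − 0.5^(32/182) = 0.11

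These shares apply only to that subgroup. In the simulations below, 2% to 8% of all patients had an event on days 29 to 60 in scenarios with early or capped stopping.

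**3. Direction of bias.** The SAP gives no expected median, event count or stopping rate for PFS or duration of response, so there is no stated figure to reproduce. The assumptions are exponential event times, 28-day assessments, an early-stop hazard of 0.002 per day, and a hazard ratio (HR) of 1, 2 or 3 after early stopping. Each scenario had 300,000 simulated patients. Censoring was either back-dated to the last assessment on or before stopping, or placed at the end of the window, which footnote 2 permits. A repeat run agreed within about 3 days.

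Medians in days, treatment until progression:

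| HR after stop | True | 28 days, back-dated | 28 days, end of window | 60 days, end of window |
|---|---|---|---|---|
| 1 | 300 | 278 | 300 | 300 |
| 2 | 252 | 265 | 285 | 274 |
| 3 | 230 | 256 | 274 | 255 |
| 1 | 540 | 498 | 541 | 541 |
| 3 | 366 | 458 | 493 | 453 |

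When stopping predicts a worse outlook, the 28-day rule overestimates the median. A 60-day window reduces that bias without removing it. When stopping is uninformative, end-of-window censoring is unbiased. Back-dated censoring then underestimates, because events in the 28 days still count while event-free patients leave the risk set earlier.

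**4. Capped treatment.** Cohort 2: 12 × 28 = 336 days. If patients stop only at the cap and the true median is 300, estimated survival at day 330 is 0.467 against a true 0.467, so there is no bias up to that point. With a true median of 540, end-of-window censoring leaves the median unreached. Back-dated censoring gives 342, because everyone event-free leaves at the cap and only those with an event in the next 28 days remain at risk.

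Time was measured from Cycle 1 Day 1. The same mechanism applies to duration of response, but no separate run was made for it.

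**The case against.** A 28-day on-treatment window can be a deliberate choice. The SAP uses the same window for treatment-emergent adverse events. Within it any death counts, OS counts deaths without it, and the efficacy listings show progression and death dates. The study is descriptive and PFS is not a Part 2 primary endpoint. All of this stands and lowers the stakes. It does not reconcile the definition with the censoring sentences, and Table 4 carries the rule into duration of response.

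The SAP also does not show that marrow or other disease assessments continue to day 60. Read literally, section 2.2.3 gives the 60 days to patients who completed treatment, so early stoppers may not be included. This stands too. How many relapses are dropped is unknown; the firmer loss is deaths recorded for OS.

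A wider window is not always closer to the truth. If censoring stays back-dated to before stopping and stopping is uninformative, moving from 28 to 60 days shifts the median from 278 to 265 (true 300). At a hazard ratio of 3 it helps: 256 becomes 233 (true 230).

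A reader might infer that both endpoints are biased upward, and that fixed treatment length is a cause. The documents do not support this. Upward bias needs stopping that is related to prognosis, which the SAP does not establish. Treatment is capped only in Cohorts 1 and 2, and censoring at a planned stop is not informative in itself. A reader might also take 31%, 22% and 11% as the share of the trial affected. They rest on assumed medians and describe only patients event-free at day 28.

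**Conclusion.** The inconsistency is certain from the text. The 28-day limit in section 7.1 and Table 4 contradicts the any-cause-death definition and does not match the sentences based on the follow-up period. The only post-dose follow-up length that the SAP states is 60 days. Known deaths and any documented relapse or progression after day 28 are dropped.

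The effect on the estimates is possible but not fixed in direction. Under the assumptions above, at a true median of 230 to 252 days it ranges from +13 days (252 to 265) to +44 days (230 to 274) when stopping is informative. It is −22 days (300 to 278) when stopping is uninformative and censoring is back-dated. Larger shifts appear at longer medians. In Cohorts 1 and 2 the main cost of censoring at the cap is lost information on later events. The point deserves correction before analysis, but it does not show that the planned results will look too favourable.

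**What to change.** Use one event window in section 7.1 and Table 4. In the main analysis of PFS and duration of response, count every documented relapse, progression or death through the end of follow-up as an event, whatever the reason for stopping. Keep the censoring that section 7.1 already states for new anti-cancer treatment and for assessment gaps over 16 weeks. Otherwise censor at the last adequate assessment, including any made during follow-up, so that censoring is not needlessly back-dated. State which patients have the 60-day follow-up and whether disease is assessed in it. Report the 28-day version as a sensitivity analysis.

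The cost is a change of SAP wording and one more analysis run, and medians may change. Events already documented need no new data. If disease is not assessed after day 28, the change will mainly recover deaths. It will not capture relapses after the end of follow-up.

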#### 7.2. Safety Endpoints

#### 7.2.1. DLT Definitions

A DLT will be classified according to NCI CTCAE version 4.03 and is defined as any of the following adverse events unless the event can clearly be determined to be unrelated to drug occurring in the first cycle of treatment (within 28 days of first dose or until patient receives a second cycle if there are treatment delays). Data from all cycles of treatment will be analyzed for safety, delayed toxicity, and cumulative toxicity.

In principle, a patient needs to be on study for at least 28 days to be evaluable for DLT observation, and may be replaced if they terminate study participation earlier than 28 days without experiencing a DLT. Patients who are not able to receive at least 80% of the planned dose of the PF-06747143 and backbone chemotherapy (in Part 2 combination study) in the DLT assessment period are considered not evaluable for DLT and will be replaced. However, in some circumstances of a clear drug unrelated event (eg, traffic accident, clear disease progression, or withdrawal of consent) that leads to study termination close to or before 28 days, the patient might be deemed evaluable if the Investigators and Sponsor agree.

In addition, patients not evaluable for assessment of DLT, as described in Section 7.2.1, may be replaced.

#### 7.2.2. MTD Definition

The MTD would be any doses with true toxicity probabilities in the Equivalence Interval (EI) where the EI is defined as [20%-30%].

In practice, the MTD will be the highest dose associated with the occurrence of DLTs  $\leq$ 33% (eg, 3/9 evaluable patients experience a DLT during the first treatment cycle).

#### 7.2.3. Maximum Permitted Dose Definition

The Maximum Permitted Dose (MPD) for Part 1 and 2 is 20 mg/kg.

#### 7.2.4. Recommended Phase 2 Dose (RP2D) Definition

The Recommended Phase 2 Dose (RP2D) is the dose chosen for further study based on Part 1 results. If the MTD proves to be clinically feasible for long term administration in a reasonable number of patients, such dose usually becomes the RP2D. Further experience with the MTD may result in a RP2D dose lower than the MTD.

#### 7.2.5. Vitals Signs

Vital signs, See Schedule of Activities in the protocol for details.

#### 7.2.6. Laboratory Data

The number and percentage of patients who experienced laboratory test abnormalities will be summarized according to worst toxicity grade observed for each laboratory assay. The analyses will summarize laboratory tests both on the entire study period and by cycle (Cycle 1 and Cycles beyond 1). Shift tables will be provided to examine the distribution of laboratory toxicities.

For laboratory tests without CTCAE grade definitions, results will be categorized as normal,

#### 7.2.7. Adverse Events

AEs will be graded by the investigator according to the CTCAE version 4.03 and coded using the Medical Dictionary for Regulatory Activities (MedDRA). The focus of AE summaries will be on Treatment Emergent Adverse Events, those with initial onset or increasing in severity after the first dose of study treatment. The number and percentage of patients who experienced any AE, SAE, treatment related AE, and treatment related SAE will be summarized according to worst toxicity grades. The summaries will present AEs both on the entire study period and by cycle (Cycle 1 and Cycles beyond 1).

#### **Treatment Emergent Adverse Events**

- All deaths from start of treatment until 28 days after the final dose.
- All treatment related SAEs.
- All unrelated SAEs from treatment start until 28 days after final dose of treatment.
- All non-fatal AEs occurring after treatment start up until 28 days after final dose of treatment or until start of new anti-cancer treatment, whichever is first.
- Disease progression is not considered a treatment emergent adverse event unless the subject dies of disease prior to 28 days after discontinuation of treatment.
- Events that are continuations of baseline abnormalities are considered treatment emergent adverse events only if there is an increase in grade over baseline.

#### **Treatment Related Adverse Events**

Treatment Related Adverse Events are treatment emergent adverse events with cause categorized by the investigator as related to study treatment. Events that are continuations of baseline abnormalities (signs and symptoms) are not considered treatment emergent, and hence are not considered treatment related, unless there is an increase in grade over baseline.

#### 7.2.8. ECG and QTc Interval

The analysis of ECG results will be based on Safety Population patients with baseline and on-treatment ECG data.

ECG measurements will be used for the statistical analysis and all data presentations. Any data obtained from ECGs repeated for safety reasons after the nominal time-points will not be averaged along with the preceding values. Interval measurements from repeated ECGs will be included in the outlier analysis as individual values obtained at unscheduled time points.

QT intervals will be corrected for heart rate (QTc) using standard correction factors (ie, Bazett's, Fridericia's and possibly a study specific factor). The adequacy of the correction method will be assessed graphically (plots of QT and QTc versus RR) and supplementary transformations may be considered, as appropriate. Data will be summarized and listed for QT, HR, RR, PR, QRS, QTcF and QTcB by treatment and dose. Individual QTc (all evaluated corrections) intervals will be listed by compound, time and dose. The most appropriate correction factor will be selected and used for the following analyses of central tendency and outliers and used for the study conclusions. Descriptive statistics (n, mean, median, standard deviation, minimum, and maximum) will be used to summarize the absolute QTc value and changes from baseline in QTc after treatment by compound, dose and by time point. For each patient and by treatment, the maximum change from baseline will be calculated as well as the maximum post-baseline value across time-points. Outlier analysis of the QTc data will be conducted and summarized as follows:

- 1. The number of patients with maximum change from baseline in QTc (<30, 30-60, and  $\ge$ 60 ms).
- 2. The number of patients with maximum post-dose (post-baseline) QTc (<450, 450-<480, 480-<500, and >=500 ms).

In addition, the number of patients with corrected and uncorrected QT values ≥500 msec will be summarized.

Shift tables will be provided for baseline vs. worst on study QTc (one or more correction method will be used) using Maximum CTC AE Grade. As well as tables of ECG abnormality at baseline (yes, no, not done: (n, %)). Patients experiencing clinically-relevant morphological ECG changes will be summarized (including frequency and percentage).

If more than one ECG is collected at a nominal time post dose (for example, triplicate ECGs), the mean of the replicate measurements will be used to represent a single observation at that time point. If any of the three individual ECG tracings has a QTc value  $\geq$ 500 msec, but the mean of the triplicates is not  $\geq$ 500 msec, the data from the subject's individual tracing will be described in a safety section of the study report in order to place the  $\geq$ 500 msec value in appropriate clinical context. However, values from individual tracings within triplicate measurements that are  $\geq$ 500 msec will not be included in the categorical analysis unless the

average from those triplicate measurements is also  $\geq$ 500 msec. Changes from baseline will be defined as the change between QTc post dose from Day 0, or the pre-dose values on Day 1.

The effect of drug concentrations on QTc change from baseline will be explored graphically. Additional concentration-QTc analyses may be performed. Data may be pooled with other study results and/or explored further with PK/PD models.

#### 7.2.9. Immunogenicity

The development of anti PF 06747143 antibodies will be measured using validated assays. Listings and summary tabulations of number of patients and incidence of ADA at baseline (pretreatment) and post treatment will be generated.

Potential impact of immunogenicity on PK and clinical responses including PD markers, safety/tolerability and efficacy of PF 06747143 will be explored, if data is warranted.

